### 3.8.3 Exploratory Efficacy Analyses

Subgroup analyses will be conducted to explore treatment differences within baseline characteristics age, gender, BMI, baseline pain, symptom duration, Kellgren-Lawrence (KL)

	EP-104IAR-201 Statistical Analysis Plan	Version: Final 1.0
	Date: 14-Jun-2023	Page 24 of 38

grade, and disease type. If >10% of the ITT population received less than 20mg of EP-104, an additional subgroup analysis of at least, or less than 20mg EP-104 will be included. An ANCOVA model with treatment and baseline WOMAC pain as covariates will be estimated for each subgroup factor at the time points Week 4, Week 8, Week 12, Week 18, and Week 24, and these analyses will be based on the ITT population. Subgroups will consist of the following:

- Age:  $\geq$  or  $<$  65 years
- Gender: Male or female
- BMI:  $\geq$  or  $<$  30 kg/m^2
- Baseline pain: Split by median WOMAC Pain
- Symptom duration: Split by median years
- KL Grade: Grade 2 or Grade 3
- Disease type: Unilateral or bilateral OA
- Dose received: <20mg or  $\geq$ 20mg (only performed if the <20mg group contains greater than 10% of the total ITT population)

Perceptions of treatment received/administered will be analyzed in the following way:

- Difference between treatment groups in patient beliefs about treatment received
  - A summary table will be used to explore the proportion of patients, within each responder category, that believe they received EP-104IAR vs. placebo. Responder categories will be based on Week 12 change from baseline WOMAC Pain as described in Section 3.8.2.
  - A summary table with reasons for belief will also be provided.
- Difference between treatment groups in physician beliefs about treatment received
  - This summary will be identical to that above, with responder categories instead based on Week 12 change from baseline MDGA. Subjects will be considered to be an X% responder if they have at least an X% decrease from baseline MDGA. Those with at least 30% decrease, at least 50% decrease and at least 70% decrease will be presented in the summary table.

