#### 3.2 Randomization

Eligible subjects will be randomly assigned to treatment and vehicle in a 1:1 allocation ratio.

 PROSOFT Clinical	EP-104IAR-201 Statistical Analysis Plan	Version: Final 1.0
	Date: 14-Jun-2023	Page 15 of 38

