### 3.3 Sample Size Considerations

This study has been sized making the following assumptions:

- Inferential testing is at the (two-sided) 5% level, and with a desired power of 80%.
- The primary endpoint is the difference between treatment groups in change from baseline WOMAC Pain (average of 5 pain items) at 12 weeks post-dose, as measured using a 0-10 scale
- The standard deviation of the endpoint is 2.2, as assessed from review of similar studies from clinicaltrials.gov
- The desired difference to detect is 0.8.

Based on these assumptions, a sample size of approximately 120 subjects per treatment group is required. Assuming a drop-out rate of approximately 20%, 150 subjects will be randomized and dosed in each treatment arm.

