### 3.7 Primary Endpoint Analysis

The primary efficacy endpoint is the difference in change from baseline between EP-104IAR and vehicle in WOMAC Pain at Week 12, in the ITT population. Baseline WOMAC Pain will be calculated at the individual level and is defined as the average of no more than three pre-dose measurements including the three scheduled measurements: 2 measurements during the Washout and Baseline Period and 1 at Visit 2 (pre-dose). If the subject has less than three pre-dose measurements, the average of all available pre-dose measurements will serve as the subject's baseline value. If a subject has more than three pre-dose measurements, then the three measurements collected immediately prior to pre-dose will be used to derive baseline WOMAC pain and earlier measurements will not contribute.

Change from individual pre-dose baseline will then be calculated for each post-dosing weekly assessment from Week 1 through Week 24. A mixed-effects model for repeated measures (MMRM) model will then be fit to the change from baseline data for all subjects in the ITT population, including fixed effects terms for: site (potentially grouped, see Section 4.2 for more details); individual baseline WOMAC Pain; and the treatment-by-week interaction, where treatment and week are both defined as categorical variables. A random per-patient intercept will also be included. An unstructured covariance matrix at the patient level will initially be fit; if this model fails to converge numerically, a compound symmetry structure will be used.

No imputation of missing data will be performed for this analysis; the MMRM model allows handling of missing data under the assumption that data is missing at random (MAR). To assess robustness to the assumption that data is missing at random, a multiple imputation approach will be used. Under this approach, outcome data will be imputed according to the following logic:

	EP-104IAR-201 Statistical Analysis Plan	Version: Final 1.0
	Date: 14-Jun-2023	Page 18 of 38

- If missing data is due to lack of efficacy (as captured by the Study Termination page on eCRF), data will be imputed as if subjects received placebo.
- If missing data is due to other reasons, data will be imputed as if subjects received their actual treatment.

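### The exploratory subgroup ANCOVAs include no treatment-by-subgroup estimate, so the plan gives no direct measure of whether the effect differs between levels

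*SAP*

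**What the plan says.** SAP 3.8.3 plans exploratory subgroup analyses in the ITT population for seven two-level baseline factors: sex, age, BMI, KL grade, baseline pain, duration of symptoms, and unilateral versus bilateral disease. An eighth split, by EP-104IAR dose received (below 20 mg or not), is added only if the low-dose group exceeds 10% of the ITT population. The model is given in one sentence: "An ANCOVA model with treatment and baseline WOMAC pain as covariates will be estimated for each subgroup factor", at Weeks 4, 8, 12, 18 and 24.

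No subgroup main effect, treatment-by-subgroup term, contrast between levels or rule for interpretation is stated. Protocol 11.7.3.2 leaves the detail of exploratory analyses to the SAP. The only interaction specified in either document is the one in the primary MMRM (SAP 3.7), whose terms include "individual baseline WOMAC Pain; and the treatment-by-week interaction, where treatment and week are both defined as categorical variables".

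Site is absent from the subgroup model. It is present in the other efficacy ANCOVAs that the SAP writes out: the multiple-imputation robustness analysis, AUC, SF-36 and rescue medication. SAP 4.3 gives no missing-data rule that covers the subgroup models.

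**The concern.** The natural question for a subgroup table is whether the treatment effect differs between levels. A model containing only treatment and baseline pain yields effects within levels only if it is fitted once per level. That produces two treatment estimates per factor and no estimate of their difference.

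With about half the sample in each level, each fit has roughly even odds of reaching significance when the true effect equals the design effect. A reader who sees a significant result in one level and not in the other may then read a real difference into chance. With seven factors, two levels and five weeks, the plan yields 7 x 2 x 5 = 70 within-level estimates (80 with the dose split), so such patterns are easy to find.

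A separate, smaller matter is that single-week fits on subjects observed that week use different covariates and a different missing-data basis from the primary MMRM. Subgroup estimates therefore need not line up with the primary estimate.

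**Working it through.** **Inputs, from SAP 3.2 and 3.3.** Two-sided 5% test, 80% power and 1:1 allocation. The target is a 0.8-point difference. The variability is taken from outside trials: "The standard deviation of the endpoint is 2.2, as assessed from review of similar studies from clinicaltrials.gov". Evaluable numbers are 120 per arm, which 20% drop-out raises to 150 per arm randomized.

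**Reproducing the plan's figure.**
- n per arm = 2 x (1.96 + 0.842)² x 2.2² / 0.8² = 119 after rounding up, against the stated 120.
- Power at 120 per arm: SE = 2.2 x √(2/120) = 0.284, and Φ(0.8/0.284 − 1.96) = 80.4% (80.1% with the noncentral t).
- 120 / (1 − 0.20) = 150 per arm. The plan's figures reproduce.

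**One 50:50 factor, uniform true effect of 0.8.** Each level has 60 evaluable per arm.
- SE per level = 2.2 x √(2/60) = 0.40.
- Power per level = Φ(0.8/0.402 − 1.96) = 51.3%.
- Both levels significant: 0.513² = 26%. Neither: 0.487² = 24%. Exactly one: 2 x 0.513 x 0.487 = 50%.

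**Sensitivity of the chance that exactly one level is significant**, p₁(1 − p₂) + p₂(1 − p₁):

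| Varied input | Value | Exactly one significant |
|---|---|---|
| Split (120 per arm) | 40:60 / 30:70 / 20:80 | 51% / 55% / 61% |
| All 150 per arm observed | 50:50 | 48% |
| SD (60 per arm per level) | 1.9 to 2.4 | 46% to 50% |
| True effect (60 per arm per level) | 0.4 / 0.6 / 1.0 / 1.2 | 28% / 44% / 42% / 26% |

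**The interaction instead.** The levels are disjoint, so the SE of the difference between level effects is √(0.402² + 0.402²) = 0.57.
- With a uniform effect, a 5% interaction test is falsely positive in 5% per factor (4.9% in simulation).
- Power for a true 0.8-point difference between levels: Φ(0.8/0.568 − 1.96) = 29%. For a 1.6-point difference: Φ(1.6/0.568 − 1.96) = 80%.

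**Seven factors at one week**, simulated as independent 50:50 splits (20,000 trials, 120 per arm, uniform effect of 0.8):
- At least one factor has exactly one significant level in about 88% of trials, with a mean of about 3.5 of 7.
- At least one false interaction occurs in 1 − 0.95⁷ = 30% (30.0% in simulation).

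**The case against.** The strongest reply is that SAP 3.8.3 sets out to describe treatment differences within levels. It does not claim to test heterogeneity and mentions no p-values for the subgroups. An estimate with its SE in each level meets that aim. Because the levels do not overlap, a reader given both estimates and both SEs can form the contrast, with the same SE of 0.57 as above. This stands. A reader might infer that the plan makes comparison of p-values the only route to judging heterogeneity, or that it cannot inform on subgroups at all. The documents support neither. What is missing is a planned and reported contrast.

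Several other objections also stand:
- The SAP does not use the words separate or complete-case. Both are inferences, from a model with no subgroup term and from the absence of an applicable imputation rule.
- The 50% arises from halving the sample and comparing significance. Fitting to observed data does not cause it.
- Leaving out site has a rationale. Pooled sites may hold as few as 16 subjects (SAP 4.2), about 8 per half before dividing by arm.
- A reader might infer that the subgroup results will misdirect the next trial. Nothing in either document says that they will drive it.
- Extending the primary MMRM is not trivial. It has 24 weekly visits, hence 24 x 25 / 2 = 300 unstructured covariance parameters, and a three-way term would give 24 x 2 x 2 = 96 cell means per factor. Non-convergence is a real risk.

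None of this supplies the missing estimate of the difference between levels.

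**Conclusion.** The point holds as a gap in an exploratory analysis. The plan specifies effects within levels but no estimate or CI for how those effects differ. If significance is compared between levels, a uniform design effect looks like a subgroup difference in about 50% of trials for an even split, against 5% per factor for an interaction test.

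The 50% is conditional. It assumes the Week 12 design values (0.8, SD 2.2, 120 evaluable per arm), a near-equal split, and a reader who makes that comparison. It falls to 26-28% at true effects of 1.2 or 0.4. Only the two median splits, baseline pain and symptom duration, are known to be about 50:50; the other level sizes are not given. The figure should not be carried over to all 70 estimates, because effects and evaluable numbers at other weeks are not stated. The seven-factor figures assume independent factors, and correlation would lower them. The outcome is taken to be WOMAC Pain, as the baseline covariate implies.

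These analyses lie outside the step-down hierarchy of SAP 3.8.1, so type I error for the primary and key secondary endpoints is untouched.

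**What to change.** For each of the seven baseline factors, fit one model with subgroup and treatment-by-subgroup terms. The simple version is a single ANCOVA at each planned week with treatment, subgroup, their interaction, baseline WOMAC Pain and pooled site. Because all subjects enter one fit, the small-cell reason for omitting site largely goes away. The alternative is the primary MMRM with the corresponding subgroup terms, if it converges; this would also align the missing-data basis with the primary analysis.

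Report the treatment difference in each level and the interaction estimate with its 95% CI, naming Week 12 as the main time point. Label the results exploratory and state that within-level p-values are not to be compared.

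Keep the dose-received split out of this model. It is not a baseline characteristic, and vehicle subjects have no EP-104IAR dose, so the interaction is not defined. If triggered, it needs its own specification.

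Cost: slightly more programming and no new data. The limits should be stated alongside the results: about 29% power for a 0.8-point difference between levels, and about a 30% chance of at least one false interaction across seven independent factors at one week. Both argue for emphasis on the estimate and CI over the p-value. Cheap improvement.

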### 3.8.4 Safety Analyses

Safety data (safety labs, cortisol, physical exam, knee exams, vital signs, ACTH stimulation test results, etc.) will be summarized for the safety population using standard summary statistics, by

	EP-104IAR-201 Statistical Analysis Plan	Version: Final 1.0
	Date: 14-Jun-2023	Page 25 of 38

treatment group. Both by time point data and change from baseline, where appropriate, will be assessed for continuous parameters. Shifts from baseline, where appropriate, will be summarized for categorical parameters. Figures will be used to display the time profiles of serum cortisol and glucose. No prospective hypothesis testing will be performed on safety parameters.

### 3.8.4.1 Adverse Events

An adverse event (AE) is any untoward medical occurrence in a subject administered a study product and which does not necessarily have a causal relationship with this treatment. An AE can therefore be any unfavorable and unintended sign (including an abnormal laboratory finding), symptom, or disease temporally associated with the use of a medicinal (investigational) product, whether or not related to the medicinal (investigational) product.

The AE reporting period begins when the subject signs the informed consent form and ends at Visit 9 (Week 24/End-of-Study/Early Exit Visit). All AEs will be captured in the eCRF. This applies to all AEs regardless of the presumed relationship to the study treatment. The verbatim term for adverse events will be classified by system organ class (SOC) and preferred term (PT). Pre-treatment AEs will be summarized overall by count and percentage. Treatment-emergent adverse events (TEAEs) will be summarized and analyzed for safety evaluations. All adverse events, including non-treatment-emergent, will be included in listings.

The summary of TEAEs will include frequencies and percentages and will be presented by treatment for the following:

- Overview of AEs
- All TEAEs by SOC and PT
- Serious TEAEs by SOC and PT
- TEAEs related to EP-104IAR by SOC and PT
- TEAEs by SOC, PT, and severity
- TEAEs of special interest by SOC and PT
- TEAEs leading to study discontinuation by SOC and PT
- TEAEs leading to death by SOC and PT.
- MRI-Related TEAEs by SOC and PT

An adverse event will be considered related to study drug if the relationship is “possible”, “probable/likely” or “definite”. The severity of an adverse event will be rated on the CRF as “Mild”, “Moderate”, or “Severe”. For the summary by severity, subjects who have multiple

	EP-104IAR-201 Statistical Analysis Plan	Version: Final 1.0
	Date: 14-Jun-2023	Page 26 of 38

occurrences of the same AE will be classified according to the worst reported severity of the AE. Similarly, for the summary by relationship to EP-104IAR, the AE will be classified according to the most related relationship.

Potential adverse events of special interest will be **assessed** as part of **an initial blinded review process as well as an unblinded medical monitor review process with a final designation of AESIs made following database lock and a Sponsor review of study data.**

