6. RANDOMIZATION, BLINDING AND UNBLINDING

6.1 Randomization

At Screening Visit 1a subjects will be assigned a unique subject identification (ID) number that will be used throughout the study. The Investigator will maintain a list of subject ID numbers and names to enable records to be found at a later date.

Randomization will take place at Visit 2, before IMP administration. Randomization will be performed centrally, based on a pre-defined computer-generated randomization list accessed via an interactive response technology (IRT) system. The IRT system will ensure random allocation of eligible subjects in a 1:1 ratio to EP-104IAR 25 mg or vehicle treatment groups.

A statistician otherwise not involved in the trial will generate the randomization scheme. The randomization list will not be available to any person involved in the conduct and evaluation of the trial until the trial database is declared clean and locked.

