- If the subject's serum cortisol is ≤ 138 nmol/L (≤ 5 μ g/dL) at **any visit** after dose administration **AND** they experience signs and symptoms of AI (see Section 10.2.5), perform the ACTH stimulation test at the **next scheduled visit**.

See [Figure 2](#) below.

During Screening, sites will receive serum cortisol results from the ACTH stimulation test directly from the central safety laboratory to determine subject eligibility. At all later timepoints serum cortisol results will be received by the unblinded Medical Monitor, who will inform the site which subjects should undergo the ACTH stimulation test. ACTH stimulation test results will be reported to the unblinded Medical Monitor for review.

[figure not shown]
Criteria for evaluating if the ACTH stimulation test response is normal or abnormal are provided in the Laboratory Manual.

If the results of the ACTH stimulation test are considered to be abnormal and the subject also displays symptoms of adrenal suppression, they should be managed accordingly and may require glucocorticoid replacement therapy (e.g., with physiologic hydrocortisone). If appropriate, such subjects should be referred to an Endocrinologist (or other appropriate specialist) for further evaluation and treatment.

The ACTH stimulation test is extremely sensitive (95% sensitivity and 97% specificity); however, this translates to a false positive result in approximately 1 out of every 20 tests. The ACTH stimulation test will be repeated at the End-of-Study Visit in any subjects with an abnormal test result at Week 12.

Subjects who are diagnosed with AI following dose administration should be managed by their Endocrinologist (or other appropriate specialist) until resolution. If the subject's AI is ongoing at their final scheduled study visit, the Investigator should follow-up with the subject approximately 3 months later, with at least 1 additional contact during that 3-month period.

Figure 2 Triggers for ACTH Stimulation Testing

Note: ACTH=Adrenocorticotrophic hormone Wk=Week.

Protocol No. EP-104IAR-201 - Version 7.0
15 Aug 2022

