11. STATISTICAL ANALYSIS

11.1 Statistical Methods

Key reporting and statistical methodologies are listed in this study protocol. In addition, a complete detailing of data presentation and analysis details will be documented in a separate SAP; that document will provide full detail of all analyses and reporting of the study data allowing for data idiosyncrasies identified on an ongoing (blinded) basis. The SAP will be finalized prior to formal study unblinding. Data presentations may be both tabular or graphical, as appropriate.

Primary presentations of data will be provided by treatment arm and then by suitable strata for the data type (e.g., planned time of assessment).

Inferential testing, where performed, will be two-sided and made at the 5% significance level.

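### The SAP fixes which adverse events count as being of special interest only after an unblinded review and database lock, so the content of one descriptive by-arm table can depend on results

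*SAP*

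**What the plan says.** SAP 3.8.4.1 lists the adverse-event summaries to be presented by treatment. They include "TEAEs of special interest by SOC and PT" alongside "All TEAEs by SOC and PT". Potential AESIs are to be assessed through a blinded first step and an "unblinded medical monitor review process with a final designation of AESIs made following database lock and a Sponsor review of study data". The SAP names no AESI terms or groupings and gives no criteria for selecting them. The protocol does not define AESIs.

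Three other provisions bear on the timing:

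- Protocol 6.1 withholds the randomization list from those conducting and evaluating the trial "until the trial database is declared clean and locked".
- Protocol 9.1.5.1.2 describes a Medical Monitor who is unblinded while the trial runs: "At all later timepoints serum cortisol results will be received by the unblinded Medical Monitor".
- SAP 3.4.2 has the violations that remove a subject from the per-protocol set settled after blind review and recorded in a memo before both unblinding and lock.

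SAP 3.8.4 and Protocol 11.8 both state that no prospective hypothesis tests will be done on safety parameters.

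**The concern.** Normally the rows of a by-arm AESI table are chosen for pharmacological or clinical reasons before anyone can see how the events fall between arms. Here the last decision on those rows comes after a review that the SAP itself calls unblinded, and at a stage when treatment codes may already be released. An event type could be designated, or left out, because of its observed split between arms. A reader who took the table as pre-specified would give it more weight than it deserves, whether it showed an imbalance or none.

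Safety is a stated secondary objective, and this is a corticosteroid depot with anticipated systemic and local risks. Protocol 2.2, 4.4, 10.1.4 and 10.2.5 already describe glucose increases, severe local inflammatory response, index-knee infection and adrenal insufficiency. A list could be drafted now without unblinded data.

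**Working it through.** **Order of events.** No figure in the plan depends on this point, so there is none to reproduce. The check compares the two data-dependent decisions in the SAP.

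| Decision | Blinded review | Final step | Relative to lock |
|---|---|---|---|
| Per-protocol exclusions (SAP 3.4.2) | Yes | Memo before unblinding | Before |
| AESI designation (SAP 3.8.4.1) | Yes, of potential AESIs | After unblinded Medical Monitor review and Sponsor review | After |

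The blinded step in 3.8.4.1 does not close the gap: it covers potential AESIs only, and nothing says that it freezes a list. The Medical Monitor review is explicitly unblinded. The Sponsor review has no stated blinding status; Protocol 6.1 shows only that codes may be available once the database is locked.

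**Illustration of size.** The question is how often chance alone would offer an imbalance that could be included or omitted.

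Inputs:
- 150 subjects per arm (SAP 3.3, planned number dosed).
- Assumed, because the documents give no values: k candidate terms, independent of each other; the same true incidence p in both arms; and five or more extra cases in one named arm as a visible imbalance.

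Formulas, with X and Y independent Binomial(150, p) counts in the two arms:
- Per term: d = P(X − Y ≥ 5), by exact enumeration.
- Across terms: P(at least one) = 1 − (1 − d)^k.

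| Incidence p | d per term | k = 5 | k = 10 | k = 20 |
|---|---|---|---|---|
| 1% | 0.0056 | 3% | 5% | 11% |
| 2% | 0.0313 | 15% | 27% | 47% |
| 3% | 0.0625 | 28% | 48% | 73% |
| 5% | 0.1152 | 46% | 71% | 91% |

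For example, at p = 3% and k = 20: 1 − (1 − 0.0625)^20 = 0.725. By symmetry, the same probability applies to the other arm.

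Five extra cases is a weak threshold: 7 versus 2 gives Fisher p = 0.17, and 5 versus 0 gives p = 0.06. With Fisher p < 0.05 in either direction as the criterion, and incidence from 2% to 10%, the chance of at least one such term is 6% to 15% for 5 candidates, 11% to 28% for 10, and 21% to 49% for 20.

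**The case against.** The strongest reply is that little depends on this table. Safety is descriptive, so no alpha, endpoint or success criterion is affected. The AESI table has the same SOC and PT layout as the full table, so a preferred term added or dropped because of its imbalance would still appear there with its counts. Serious, related, severity, discontinuation and death tables are also planned by arm, whatever is designated an AESI. Cortisol, ACTH test and knee-examination results have summaries of their own. All of this stands, and it is why the point is minor.

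The text is also less definite than it may seem. It does not say whether designation applies to terms or to individual events. If it is event-level, the unblinded Medical Monitor may be needed because that role receives the cortisol and ACTH results withheld from sites; the word unblinded does not by itself show that arms are compared. This stands too. It does not remove the need for criteria fixed in advance: event-level designation would be harder to audit from the summary tables.

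A reader might infer three stronger things that the documents do not support:

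- **That the Sponsor chooses the list knowing allocation.** The SAP says only "final designation of AESIs made following database lock and a Sponsor review of study data"; it does not say that this review is unblinded or by arm.
- **That the safety results become uninterpretable.** The complete by-arm tables prevent that.
- **That Protocol 11.1 is breached.** It says "The SAP will be finalized prior to formal study unblinding", and a SAP finalised on time can still describe a later designation step.

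Finally, the illustration describes chance imbalance among many terms, which arises whenever AESIs are designated. Late designation adds only the opportunity to choose among them.

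**Conclusion.** The point holds in a limited form. The SAP leaves the content of a planned by-arm AESI table open until after an unblinded review, database lock and a Sponsor review of data, with no list or criteria set beforehand. That content can therefore depend on results by arm, whereas the per-protocol exclusions are fixed while blind. Nothing shows that it will be shaped in this way, and no intent is implied.

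The consequence is confined to how far one descriptive table can be read as pre-specified. The opportunity for selection runs from about 3% (5 terms, 1% incidence) to about 91% (20 terms, 5% incidence). No single value in that range should be quoted as the size of the problem, because the number of terms, their incidence, their independence and the five-case threshold are all assumptions. The timing and the lack of a list are clear from the text; the blinding of the Sponsor review and the unit of designation are not. Severity: minor.

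**What to change.** In SAP 3.8.4.1, state whether AESIs are designated by term or by event. Fix the preferred terms or groupings, or the event-level criteria, at the blinded review, and record them in a dated memo before database lock and unblinding, as is done for the per-protocol set. Label anything added later as post hoc and show it in a separate table, so that an unexpected signal can still be reported. State also whether the Sponsor review is blinded.

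The cost is a few sentences in the SAP and a sign-off at a review that is already planned. No data collection, visits, subjects or clinical management change. Label: free improvement.
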